#### 1.8.6 Gene Expression Profiling in Metastatic Melanoma

High-throughput gene expression profiling has recently discovered several important findings in patients with melanoma.(49-53). Next-generation sequencing (NGS) technology using RNA sequencing (RNA-Seq) provided unbiased determinations of RNA transcript enrichment and detection of novel transcripts with high sensitivity and specificity. It also gave broader dynamic range of detection and allowed detection of rare and low-abundance, yet potentially important, transcripts from the RNA samples. Information on gene expression profiling including the level of expression, landscape of transcript isoform variants, and the enrichment of specific RNA isoforms affect melanoma tumorigenesis, organ-specific metastasis, malignant transformation and inform intratumoral heterogeneity (54-56). This information is unobtainable by standard exome or genome sequencing alone. Additionally, Van Allen demonstrated that prediction of neoantigen peptides based on WES alone overestimated 6320 neoantigens without RNA-sequencing data, and missed 166 neoantigen that are expressed in the tumor, likely due to post-transcriptional RNA processing. Moreover, the authors found that a large proportion of neoantigen predicted by WES are expressed at negligible levels in the patients' tumors as determined by the TCGA database(48).

While considerable information from RNA-Seq expression and methylation data are available

for cutaneous melanoma from the Cancer Genome Atlas (TCGA) database and other publicly available domains, including remarkable sub-classification of cutaneous melanoma according to their transcriptomic expression levels and patterns (57), there is no transcriptomic information on MCM and ALM gene expression available in literature.

#### **1.8.7 Gut Microbiota and Immune Checkpoint Inhibitor Therapy**

Recent breakthrough studies have demonstrated that, in mouse models, certain intestinal microbiomes, i.e. *Bacteroides fragilis* and *Bifidobacterium* sp. altered the response of cutaneous melanoma in mouse model to the anti-PD-1 and anti-CTLA-4 monoclonal antibodies. Further studies into *Bifidobacterium* demonstrated that the bacteria alters dendritic cell activity, which led to improvement of tumor-specific CD8+ T cell activity, and delays in melanoma growth (58, 59). It is not clear whether intestinal microbiomes in variant melanoma have similar or distinct immunomodulatory effects against tumor and affect the activity of immune checkpoint blockades.

#### **1.8.8 Circulating Cell-Free Tumor Mutant DNA in Metastatic Melanoma**

Successful techniques of circulating cell-free tumor-specific mutant DNA recovery have been established with various detection methods, from restriction enzyme digestion and selective priming of mutant alleles (60), BEAMing (Beads, Emulsion, Amplification, and Magnetics) (61), and droplet digital PCR (ddPCR) (62) in cutaneous melanoma with known driver *BRAF*, *NRAS* or *KIT* mutations. However, identifiable driver mutations are detected in only 10-30% of variant melanoma, identification of potential circulating tumor-specific mutant DNA as circulating biomarkers in variant melanoma whose tumors are often identified as *BRAF/NRAS/KIT*-wild type is an unmet need.

### **1.9 Study Rationale**

Immunotherapy with HD-IL-2 has produced durable benefit in 10% of patients with metastatic cutaneous melanoma. The antitumor activity of IL-2 has been limited at least in part by immunosuppressive and immune-regulatory forces within the tumor microenvironment. Antibodies against CTLA4 (e.g. ipilimumab), PD1 and its ligand (PD-L1) produced long-term benefit in approximately 20-40% of patients with advanced melanoma. In addition, PD1 pathway blockers have shown anti-tumor activity in a variety of advanced solid tumors, including renal cell carcinoma, non-small cell and small cell lung carcinoma, bladder cancer, head and neck cancer, Merkel cell carcinoma and a rapidly expanding list of other tumors. In addition, the combination of ipilimumab with the anti-PD1 antibody, nivolumab, has shown tumor responses in up to 60% of patients with advanced melanoma (34). These findings have led to FDA approval of ipilimumab and nivolumab as an indication for treatment of patients with advanced melanoma and nivolumab for treatment of patients with advanced non-small cell lung carcinoma, with approvals of nivolumab and other PD1 pathway blockers either alone or in combination anticipated in other cancer types in the near future. While these data are exciting, few if any patients enrolled to this study had metastatic MCM or ALM. Only two retrospective analyses evaluated the efficacy of ipilimumab in patients with MCM with the overall objective response rate of 6-10% (35, 36), with no prospective immunotherapy studies conducted in MCM or ALM-specific population. Therefore the activity of the ipilimumab + nivolumab combination in these

subsets or patients remains unknown

Reliable predictive biomarkers for the use of immune checkpoint inhibitors are needed to identify pretreatment those patients most likely to respond and early on in treatment assays could help identify mechanisms of tumor response and resistance necessary to improve therapy. Although tumor PD-L1 expression in tumor confers higher treatment response rate, responses to nivolumab or nivolumab + ipilimumab alone were noted in 55% and 41% of patients, respectively, with PD-L1- tumors (63). Therefore, more reliable predictive biomarkers are needed.

Recently, extensive studies on metastatic colorectal cancer have demonstrated that a new scoring system as well as density of immune cells infiltrates at the center of the tumor and its invasive margin, described as Immunoscore, could accurately separate a group of patients with high Immunoscore with improved DFS, and OS from those with low Immunoscore where the histopathological staging system cannot. A recent study has also demonstrated relationship between degree of pre-treatment CD8+ tumor infiltrating lymphocytes (TILs) infiltration and PD-L1 expression at the invasive margin of the advanced cutaneous melanoma and improved long-term clinical benefits in patients with advanced melanoma who received Pembrolizumab monotherapy (47). Further, there appeared to be an association between tumor response and clonality of the immune infiltrate based on a next-generation sequencing method used to evaluate T-cell receptor rearrangement pre- and in response to checkpoint inhibitor therapy. Also, high mutational burden correlated with overall survival in patients with cutaneous melanoma treated with ipilimumab or lung cancer treated with anti-PD1. However, the biology of MCM and ALM are distinct from cutaneous melanoma at multiple levels as mentioned in Section 1.2.1 & 1.2.2. Consequently, the utility of predictive biomarkers developed for cutaneous melanoma remains unknown

### 1.10 Research Hypothesis

Treatment with nivolumab in combination with ipilimumab in patients with advanced MCM will result in an objective response rate of >25% with 90% confidence.

## **2.0 OBJECTIVES**

### Primary Objectives

2.1 To assess objective response rate (ORR, defined as complete response [CR] + partial response [PR] per investigator-assessed RECIST 1.1 criteria in patients with mucosal melanoma (MCM)

### Secondary Objectives

2.2 To assess objective response rate (ORR, defined as complete response [CR] + partial response [PR] per investigator-assessed RECIST 1.1 criteria in patients with acral lentiginous melanoma (ALM)

2.3 To determine progression-free survival (PFS), and overall survival (OS) in each cohort

2.4 To determine whether pre-existing immune cells infiltrate, as well as Ki-67 and PD-L1 expressing cells at the invasive tumor margin correlate with clinical response to a combination of CTLA-4 and PD-1 blocking therapy

2.5 To evaluate subject's cancer genomic landscape using whole exome sequence profiling, identify the mutational pattern, and the frequency of somatic mutations and their relationship to tumor response in MCM and ALM, as well as subject's cancer genomic landscape using whole exome sequence profiling and utilize bioinformatic tools to translate mutations in exomes to identify specific driver mutations in MCM and ALM

#### Exploratory Objective

2.6 To evaluate tumor's putative neoantigen epitopes from le exome sequencing data and determine binding affinity to MHC class I molecules as a potential predictor of response to combined checkpoint inhibitors treatment

2.7 To determine clonal preservation, expansion, and selection of T-cell receptor rearrangement of tumor infiltrating lymphocytes before and after treatment with combined ipilimumab/nivolumab therapy as a correlative biomarker of treatment response

2.8 To identify MCM and ALM gene expression profiling pattern associated with treatment response or resistance to combined checkpoint inhibitors treatment

2.9 To identify relationship of specific gut microbiota in MCM and ALM with CD8+T cell function and anti-tumor immunity

2.10 To identify circulating cell-free nucleic acids and its pattern that might be associated with combined checkpoint inhibitor treatment response/resistance in order to further narrow the application of combined checkpoint inhibitors to those who will benefit the most

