### 9.3.1 Assessment of Pretreatment and Serial Levels of Circulating Cell-Free Nucleic Acids

All patients will have plasma and serum collected at pre-treatment, every 6 weeks on-treatment, and at PD. Guidelines for isolation of plasma and serum are outlined in Section 9.3. Each sample will be linked to the corresponding tumor and labeled with non-identifiable coding system designated for each tumor.

Information on mutant DNA enriched in each tumor will be extracted from WES analyses. The analysis will assess circulating cell-free mutant DNA from the top most enriched mutations in each patient's tumor, in addition to a panel of cancer related genes. Circulating cell-free mutant DNA analysis will be performed on Illumina HiSeq system with TruSeq Nano Sample Preparation Kit (or equivalent system) to detect and quantify the circulating mutation load per ml of serum. The frequency of circulating mutant DNA will be assessed at baseline, at 6 weeks interval, and at RECIST-defined disease progression. The kinetics of circulating cell-free mutant DNA compared to baseline will be compared with radiographic response (per RECIST v.1.1) to establish the relationship between circulating mutant DNA burden and response to combined immune-checkpoint blockade.

Serum samples from each patient may be used to analyze for circulating non-coding RNA (i.e. miRNA) and exosomal substrates (i.e. protein, miRNA, snRNA)

We will attempt to establish predictive circulatory biomarker that could separate responders from non-responders in MCM and ALM cohorts

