## 10.3 Statistical Analysis for Correlative Studies

### 10.3.1 Best Overall Response

The proportion of patients achieving a response (best overall response; complete or partial response as per RECIST v1.1 criteria (outlined in appendix C) and exact binomial 95% CI will be calculated. Objective response rates (complete response + partial response) will be calculated separately for each cohort.

Among all enrolled patients, additional hypothesis-generating analyses will be undertaken to explore whether somatic mutational loads, difference in driver mutation profiles, level of pre-treatment CD8+ TIL and PD-L1 expressing cells at the invasive tumor margin, presence of tumor specific neoantigen, TCR clonality, gene expression profiles and enrichment of specific gut microbiota might be associated with responsiveness in order to further refine the optimal population for treatment with ipilimumab and nivolumab combination in MCM and ALM.

Categorical factors and continuous factors will be compared between responders and non-responders using Fisher's exact tests and two-sample Wilcoxon rank sum test respectively.

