### 10.3.2 Time to Event

Progression-free survival, response interval and overall survival will be summarized using the Kaplan-Meier method.

Progression-free survival is defined as the time from the date of treatment initiation until the date that disease progression criteria are met or the date death without progression, or is censored at the date of last disease assessment without evidence of progression.

Response interval is defined among patients achieving a complete or partial response, from the date that response is achieved until the date that disease progression criteria are met or death without progression, or is censored at the date of last disease assessment without evidence of progression.

Overall survival is calculated from the date of treatment initiation to the date of death, or censored at date of last contact.

The association between somatic mutational load and time to event outcome in MCM and ALM can be assessed using log rank tests. Kaplan-Meier curves by mutation status will be presented.

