## **11.0 RECORDS TO BE KEPT**

The original signed consent form will be kept with the patient's other study documentation (e.g., the hospital or clinic chart, the case report form).

A data manager will be assigned to this protocol to ensure that data is collected and reviewed on a continuous basis.

The following forms will be submitted to the electronic data capture (eDC) system:

Forms:

- 1) Patient Registration Form
- 2) **On-Study Form** (within 2 weeks after initiation of treatment)
- 3) **Measurement Form** (at baseline and then every 12 weeks) until treatment completion. For patients with persistent SD or response at time of treatment discontinuation, subsequent imaging will be every 3 months until 2 years from treatment initiation, then every 6 months during year 3, and then yearly thereafter for years 4 and 5 per standard of care)
- 4) **Treatment Form (within 4 weeks of decision to stop treatment for each subject)**  

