and measured at baseline. Target lesions should be selected on the basis of their size (lesions with the longest diameter), be representative of all involved organs, but in addition should be those that lend themselves to reproducible repeated measurements. It may be the case that, on occasion, the largest lesion does not lend itself to reproducible measurement in which circumstance the next largest lesion which can be measured reproducibly should be selected. A sum of the diameters (longest for non-nodal lesions, short axis for nodal lesions) for all target lesions will be calculated and reported as the baseline sum diameters. If lymph nodes are to be included in the sum, then only the short axis is added into the sum. The baseline sum diameters will be used as reference to further characterize any objective tumor regression in the measurable dimension of the disease.

Non-target lesions. All other lesions (or sites of disease) including any measurable lesions over and above the 5 target lesions should be identified as non-target lesions and should also be recorded at baseline. Measurements of these lesions are not required, but the presence, absence, or in rare cases unequivocal progression of each should be noted throughout follow-up.

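### No planned analysis can tell whether an association between pre-treatment circulating DNA and response merely reflects tumor burden

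*Combined protocol and SAP*

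**What the plan says.** Objective 2.10, an exploratory objective, is "To identify circulating cell-free nucleic acids and its pattern that might be associated with combined checkpoint inhibitor treatment response/resistance". Its stated purpose is to restrict the combination to the patients who gain most. Section 9.3.1 plans to "detect and quantify the circulating mutation load per ml of serum" before treatment, every 6 weeks and at progression. It hopes to find a circulating marker that distinguishes responders from the rest, and it also plans to set change from baseline against radiographic response.

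Section 10.3.1 states the marker tests: factors are "compared between responders and non-responders using Fisher's exact tests and two-sample Wilcoxon rank sum test". It introduces them as "additional hypothesis-generating analyses will be undertaken to explore whether somatic mutational loads" and a list of other factors relate to response. Circulating nucleic acids are not in that list. For survival outcomes, section 10.3.2 says: "The association between somatic mutational load and time to event outcome in MCM and ALM can be assessed using log rank tests". No covariate, stratification or multivariable model is given for any marker.

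Tumor burden is available. Section 3.1.2 requires measurable disease. Under Appendix D, section 1, a sum of diameters "for all target lesions will be calculated and reported as the baseline sum diameters". Section 11.0 requires a Measurement Form at baseline.

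**The concern.** A load per ml is an amount of tumor-derived material, so it is the marker in this plan most likely to follow how much tumor a patient has. If patients with more tumor also respond less often, the pre-treatment level will differ between responders and non-responders even when it adds nothing to the baseline scan. That difference is a true association, but it is not evidence that the assay adds information, and added information is what choosing patients with it requires. The plan measures both quantities and never puts them in one model.

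**Working it through.** **The plan's own figures.** The documents give no figure for the marker analyses, so the check starts from section 10.2. With 39 evaluable patients, success needs at least 14 responses:
- P(X ≥ 14 | 39, 0.25) = 0.0862
- P(X ≥ 14 | 39, 0.45) = 0.905
- 39/(1 − 0.20) = 48.75, rounded up to 49

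All three agree with the plan.

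**Patients available to a marker test.** Cohort A has 39. Pooling cohort B at the same 20% loss gives 39 + 0.80 × 24 = 58.2, about 58. Responders among 39 number 0.25 × 39 = 9.75 (about 10) to 0.35 × 39 = 13.65 (about 14).

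**Assumptions, none of them in the documents.** Burden B is standard normal. The marker is M = ρB + √(1 − ρ²)·e, with e standard normal. Response follows logit P = a + log(OR)·B, so M has no effect once B is known. The constant a gives 35% responders, between the plan's 25% null and 45% alternative, unless noted. The rank-sum test at two-sided 5% is compared with a likelihood-ratio test of M in a logistic model containing B. Each setting has 2,000 simulated trials, so the simulation error is at most √(0.25/2000) = 1.1 points. Ranges in the table come from repeated runs.

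| Patients | OR per SD of burden | ρ | Unadjusted p<0.05 | Adjusted, burden known exactly |
|---|---|---|---|---|
| 39 (45% responders) | 0.7 | 0.3 | 5% | 5% |
| 39 | 0.5 | 0.6 | 18% | 6% |
| 39 | 0.5 | 0.8 | 29–30% | 7% |
| 39 | 0.4 | 0.8 | 42–44% | 6% |
| 58 | 0.5 | 0.6 | 23–26% | 6% |
| 58 | 0.4 | 0.8 | 59–62% | 5–6% |

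If burden is unrelated to response (OR 1.0), the unadjusted rate stays at 4–5%. The response rate matters less: with 39 patients, OR 0.5 and ρ 0.7, the change is 20% to 8% at 25% responders and 24% to 6% at 45%. The 8% arises with about 10 responders, where ordinary logistic regression is slightly liberal.

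**Imperfect burden measure.** The target sum covers at most 5 lesions, 2 per organ. If its reliability for total burden is 0.6, the adjusted rate in the OR 0.4–0.5, ρ 0.6–0.8 settings is 9–24%.

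**Requiring an adjusted p<0.05.** Take a marker with a real effect of its own: marker OR 0.5 per SD, burden OR 0.5, ρ 0.6–0.8, 39 patients. It is flagged in about 75–83% of trials unadjusted, in 22–31% adjusted for exact burden, and in about 55% adjusted for a noisy sum.

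**The case against.** The best reply is that the plan claims little. Section 10.3.1 calls these analyses hypothesis-generating, section 10.2 treats the biomarker data as mainly descriptive, and no 5% rule for declaring a marker is stated. Objective 2.10 asks what might be associated with response, and a marker that tracks burden is associated. This stands. It limits the seriousness of the point, but it does not supply an analysis that bears on patient selection.

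A second reply is that circulating DNA is missing from the factor list in section 10.3.1, so applying the Fisher and rank-sum sentence to it is an inference. That is correct: it is the only sentence that could apply, and the gap should be closed. Section 9.3.1 also plans change from baseline, which uses each patient as their own reference and is less exposed to burden. But it has no named test, and a change on treatment cannot select patients before treatment.

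Three stronger readings are tempting, and the documents do not support them:
- *A burden marker will be reported as a response marker.* This needs burden to predict response and the marker to track burden. The documents quantify neither, and under weak links there is no inflation.
- *Every listed marker is compromised.* Nothing in the documents ties the others to the sum of diameters. Mutational load, for instance, is counted per megabase (section 9.2.3).
- *Only burden-adjusted associations should count.* With 10–14 responders, that rule would discard most truly independent markers even if burden were measured exactly.

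**Conclusion.** The point holds for the pre-treatment level of circulating mutant DNA. The plan has only unadjusted tests, the burden measure is already collected, and no planned analysis separates the two explanations of an association. The chance that a burden-only marker reaches p<0.05 lies between about 5% and 60%, depending wholly on the assumed burden–response odds ratio and marker–burden correlation. Adjustment reduces that chance but does not remove it unless burden is measured well. This is a worthwhile improvement to an exploratory analysis. It does not touch the primary ORR test or the sample size.

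**What to change.** In section 10.3.1:
- Name pre-treatment circulating mutant DNA as a factor and state its test.
- Beside that test, report a Firth-penalized logistic estimate with confidence interval for the marker on the log scale, adjusted for log baseline sum of target diameters. Add a cohort term when cohorts are pooled. State how undetectable levels enter the log.
- If the marker is analysed against PFS or OS, use the Cox equivalent.
- Describe the adjusted estimate as showing whether the marker appears to add to burden. Do not make it a condition for calling a marker associated.
- Offer the same model for the other markers as an optional sensitivity analysis.
- Fix one definition of the baseline sum. Appendix D section 1 allows nodal short axes in it, while section 3.2 can be read as treating pathological nodes as non-target.

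The cost is SAP wording and a little code, with no new data, visits or patients. The intervals will be wide with about 10–14 responders in 39 patients, and some confounding will remain because the target sum measures total burden imperfectly. The simulations used ordinary logistic regression; the Firth version is proposed for the small responder count and was not itself simulated.

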## **3.0 SELECTION OF PATIENTS**

### **3.1 Eligibility Criteria**

- 3.1.1 Patients must have histologically confirmed MCM or ALM that is metastatic or unresectable.
- 3.1.2 Patients must have measurable disease and be eligible to receive nivolumab in combination with ipilimumab treatment per institutional guidelines.
- 3.1.3 Patients must have a tissue block (or 26 unstained slides) available with adequate tumor to perform multiplex immunohistochemistry and nucleic acids analyses (i.e. whole exome sequencing) Patients with only a previous fine-needle aspirate are ineligible for enrollment.
- 3.1.4 Patients must be willing to donate a small amount of whole blood prior to treatment and during treatment for laboratory analysis.

- 3.1.5 Patients must give informed consent prior to initiation of therapy.
- 3.1.6 Patients must be ambulatory with good performance status (ECOG 0 or 1)

